- p: A blood sample will be collected at Baseline and stored. This sample may be used for exploratory biomarkers associated with study drug or disease, or in the event that the subject develops TEAEs that warrant further investigation (eg, treatment-emergent infection), these samples may be tested to determine whether the subject already had prior exposure to any suspected infective agents.
- q: Viral characterization will include testing for previous exposure to CMV, HSV1, HSV2, etc.
- r: Centralized skin assessments using standardized photography will be conducted by a reviewing dermatologist. These assessments will specifically include evaluation of any areas of depigmentation or any rash. See [Section 9.5.1.5.8](#) for further details.
- s: To be performed by either a neurologist or a physician with comparable training and experience in undertaking neurologic examinations. [Section 9.5.1.5.9](#) details what is included in the neurological examination. The Brief Smell Identification Test (Sensonics Inc.) will be administered at the same visits and serves as part of the neurological examination. (revised per Amendment 04)
- t: An ophthalmic examination will be conducted at Visit 2 unless the subject has had a comprehensive eye exam within the past 12 months, from which a report is available. The ophthalmic examination should include funduscopy to look at the optic disc, macula and the rest of the retina as well as an assessment of visual acuity and visual fields.

Table 7 Schedule of Procedures/Assessments in Study 202: Randomization Phase (Visit 3 through Visit 20)

| Phase Period | Randomization | | | | | | | | | | | | | | | | | | | | ED _b | Follow-Up | | | | UNS Visit ^d | Interim Safety Visit |
|--|----------------|---|----|----|----|----|----|----|----|-----|-----|-----|-----|-----|-----|-----|----|-----------------|-----------------|-----------------|-----------------|----------------|----------------|---|--|---------------------------|----------------------------|
| | Treatment | | | | | | | | | | | | | | | | W2 | 19 ^c | W8 | 20 ^c | | | | | | | |
| Visit ^a | 3 | 4 | 5 | 6 | 7 | 8 | 9 | 10 | 11 | 12 | 13 | 14 | 15 | 16 | 17 | 18 | | W2 | 19 ^c | W8 | 20 ^c | | | | | | |
| Day | 1 | 8 | 15 | 22 | 29 | 43 | 57 | 71 | 85 | 113 | 141 | 183 | 274 | 365 | 456 | 547 | | 561 | 575 | 589 | 631 | | | | | | |
| Week | 1 | 2 | 3 | 4 | 5 | 7 | 9 | 11 | 13 | 17 | 21 | 27 | 40 | 53 | 66 | 79 | | 81 | 83 | 87 | 91 | | | | | | |

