| Weeks elapsed since first dose | 0 | 1 | 2 | 3 | 4 | 6 | 8 | 10 | 12 | 16 | 20 | 26 | 39 | 52 | 65 | 78 | | 80 | 82 | 86 | 90 | | | | | | |
| Nominal months elapsed since first dose | 0 | | | | 1 | | 2 | | 3 | 4 | 5 | 6 | 9 | 12 | 15 | 18 | | | 19 | | 21 | | | | | | |
| Procedures/ Assessments | | | | | | | | | | | | | | | | | | | | | | | | | | | |
| Routine physical examination | X | | | | X | | X | | X | | | X | X | X | X | X | X | | X | | X ^c | X | | | | | |
| Inclusion and Exclusion criteria | X | | | | | | | | | | | | | | | | | | | | | | | | | | |
| Vital signs ^l | X | X | X | X | X | X | X | X | X | X | X | X | X | X | X | X | X | X | | X | | X ^c | X | X | | | |
| Respiratory rate | | | | | X | | X | | X | X | X | X | X | X | X | X | X | | X | | X ^c | X | | | | | |
| Weight | | | | | | | | | X | | | X | X | X | X | X | X | | | | | X | X | | | | |
| Centralized dermatological assessment via photography ^g | | | | | | | | | X | | | X | X | X | X | X | X | | | | | X | X | | | | |
| Neurological examination ^h | | | | | | | | | | | | X | | X | | X | X | | X | | X | X | | | | | |
| Ophthalmic examination ⁱ | | | | | | | | | | | | | | | | | | | | | | X | | | | | |
| Concomitant medications ^l | | X | X | X | X | X | X | X | X | X | X | X | X | X | X | X | X | | X | | X | X | X | | | | |
| 12-lead ECG ^k | | | X | | X | | X | | X | | | X | | X | | X | X | | X | | X ^c | X | | | | | |
| Clinical biochemistry and urinalysis | | | X | | X | | X | | X | | | X | X | X | X | X | X | | X | | X | X | | | | | |
| Complete blood count | | X | X | X | X | X | X | X | X | X | X | X | X | X | X | X | X | X | X | X | X | X | X ^l | X | | | |
| Blood samples (lymphocyte subset analyses) ^l | | X | X | X | X | X | X | X | X | X | X | X | X | X | X | X | X | X | X | X | X | X | X ^l | X | | | |
| Blood samples (Igs) ^m | | | | | X | | X | | X | | | X | | X | | X | X | | X | X | X | X | | | | | |
| Blood samples (isolation of PBMCs) | | | X | | | | | | X | | | | | | | | | | | | | X | | | | | |
| Urine pregnancy test (females of CBP only) | X ⁿ | | | | | | | | X | | | X | X | X | X | X | X | | X | | | X | | | | | |
| Blood sample (storage for immune status) ^o | | | | | X | | | | X | | | X | | X | | X | X | | X | | X | X | | | | | |
| CBB and ISLT ^p | | | | | | | | | X | | | X | X | X | X | X | X | | X | | X | | | | | | |
| MMSE ^p | | | | | | | | | X | | | X | X | X | X | X | X | | X | | X | | | | | | |

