| Randomization | X | | | | | | | | | | | | | | | | | | | | | | | | | | |
| Dispense study drug ^x | X | X | X | X | X | X | X | X | X | X | X | X | X | X | X | X | | | | | | | | | | | |

Footnotes for Table 7

ADAS-cog₁₄ = Alzheimer's Disease Assessment Scale - Cognitive subscale (14 items), CBB = CogState Brief Battery, CBP = childbearing potential, CDR = Clinical Dementia Rating scale, CSF = cerebrospinal fluid, C-SSRS = Columbia Suicide Severity Rating Scale, ECG = electrocardiogram, ED = Early Discontinuation, FAQ = Functional Assessment Questionnaire (also known as the Functional Activities Questionnaire), Ig = immunoglobulin, ISLT = International Shopping List Task, LP = lumbar puncture, MMSE = Mini Mental State Examination, MRI = magnetic resonance imaging, PBMC = peripheral blood mononuclear cell, PD = pharmacodynamics, PET = positron emission tomography, PK = pharmacokinetics, UNS = unscheduled, W2 = new Week 2 follow-up visit, W8 = new Week 8 follow-up visit. (revised per Amendment 04)

- a: Visit 3 should be conducted no more than 10 days after completion of the Baseline visit (Visit 2) assessments and confirmation of eligibility to continue in the study, unless additional time is required to take Exclusion Criterion #20 into account. (revised per Amendment 02) A window of ± 3 days will be permitted for Visit 4 to 14 inclusive. A window of ± 10 days will be permitted for Visit 15 to 18 inclusive. A window of ± 3 days will be permitted for the Follow-Up Visits. If use is made of the permitted visit windows, every effort should be made to bring the subject back in line with the "weeks elapsed since first dose" at subsequent visits.
- b: Subjects who discontinue taking study drug prematurely for any reason will undergo an ED Visit within 7 days of their last dose of study drug. In addition, Follow-Up Visits will be scheduled 2, 4, 8, and 12 weeks after the last dose of study drug (Visit W2, 19, W8, and Visit 20, respectively). (revised per Amendments 04 and 05)
- c: All subjects, regardless of whether they complete all 18 months of treatment or discontinue study drug prematurely, will complete 4 post-treatment Follow-Up visits; 2, 4, 8, and 12 weeks after the last dose of study drug (Visits W2, 19, W8, and 20, respectively). If clinically indicated, more frequent safety assessments can be made as UNS assessments or visits during the post-treatment Follow-Up period. (revised per Amendment 04)

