Complete blood counts and lymphocyte subset absolute counts and percentages will be measured (by a centralized laboratory) every week for the 1st month, every 2 weeks for the next 2 months (Months 2 and 3) and monthly for the next 3 months (Months 4, 5, and 6). Thereafter, they will be monitored every 3 months until the end of the Treatment Period and at all 4 Follow-Up Visits at 2, 4, 8, and 12 weeks after the last dose of study drug. Serum IgG, IgA, and IgM will be monitored monthly for the 1st 3 months, at 6, 12, and 18 months, and at the Follow-Up Visits that occur 4, 8, and 12 weeks after the last dose of study drug. (revised per Amendment 04)

Peripheral blood mononuclear cells (PBMCs) will be collected at Baseline, during treatment, and

post-treatment for exploratory immunomodulatory and immune-based analyses.

Centralized skin assessments, using standardized photography, will be conducted by a reviewing dermatologist at baseline and at 3-month intervals during the Treatment Period. These assessments will specifically include evaluation of any areas of depigmentation or rash. Subjects will also be questioned by the investigator at each visit to identify any changes that might represent a drug-induced rash/reaction or infection. Subjects and their caregivers/ informants will be instructed to contact the investigator if they see any lesions or other symptoms that might be associated with a drug-induced rash/reaction or infection, so such AEs can be reviewed promptly.

Baseline and on-study blood and DNA samples will be taken and stored for all subjects, and CSF samples will be taken and stored for all subjects from whom CSF samples were collected (revised per Amendments 02 and 04). These samples may be tested for exploratory biomarkers associated with study drug or disease, or in the event that a subject develops AEs that warrant further investigation (eg, to test if a subject with a treatment-emergent infection was exposed to any suspected infective agents before treatment with study drug).

Safety brain MRI assessments will be performed at Screening, at 6, 12, and 18 months during the Treatment Period and at the final Follow-Up Visit. Additional safety MRI scans are to be performed as clinically necessary. MRI acquisition and interpretation will be organized centrally to ensure reproducibility and consistency between units involved.

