9.1.2 Randomization Phase

Subjects who complete the Baseline Visit assessments, and are eligible based on the inclusion and exclusion criteria (see [Section 9.3.1](#) and [Section 9.3.2](#)), will begin the Randomization Phase no more than 10 days after completion of the Baseline Visit assessments and confirmation of the eligibility of the subject based on the results of all the Baseline Visit assessments (revised per Amendment 02).

The Randomization Phase will consist of a Treatment Period of 78 weeks duration and a Follow-Up Period of 12 weeks after the last dose of study drug.

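### In Table 7 the Day row dates follow-up Visit W8 six weeks after Visit 18, while the week rows, footnotes and text put it eight weeks after last dose

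*Protocol*

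**What the plan says.** Table 7 heads each visit with a Day, a Week and a count of weeks elapsed since first dose. From Visit 17 onward, with a blank for the early-discontinuation column, the three rows read:

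- Day: "456 | 547 | | 561 | 575 | 589 | 631"
- Week: "66 | 79 | | 81 | 83 | 87 | 91"
- Weeks elapsed: "65 | 78 | | 80 | 82 | 86 | 90"

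The last four entries in each row are Visits W2, 19, W8 and 20.

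Footnote c ties those visits to the last dose: "2, 4, 8, and 12 weeks after the last dose of study drug (Visits W2, 19, W8, and 20, respectively". Footnote b and Section 9.5.5 give the same mapping, and the abbreviation note under the table defines W8 as the Week 8 follow-up visit. Footnote a sets the tolerance: "A window of ± 3 days will be permitted for the Follow-Up Visits".

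Section 9.1.2 describes "a Treatment Period of 78 weeks duration and a Follow-Up Period of 12 weeks after the last dose of study drug". The synopsis schedules blood counts and lymphocyte subsets "at all 4 Follow-Up Visits at 2, 4, 8, and 12 weeks after the last dose of study drug". Sections 9.1.2.2, 9.1.2.3, 9.2.5 and 9.3.3 repeat the 2, 4, 8 and 12 week timing.

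**The concern.** Day 589 disagrees with the other two entries in its own column and with every written statement of when W8 takes place. The Day row is part of the operative visit schedule, so it is a plausible source for a site calendar or for EDC visit windows.

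Table 7 schedules the complete blood count, lymphocyte subsets, immunoglobulins and adverse events at W8. Safety, including immunological and hematological parameters, is the primary objective (Section 8.1). The Amendment 04 change history says that the extra follow-up draws were added to assess immunological changes after study drug ends. Under Section 9.7.1.8.3 laboratory values are summarized by visit and treatment group, and mean lymphocyte subsets are plotted over time by dose. If some W8 samples were drawn at 6 weeks and others at 8, one nominal time point would mix two times since last dose, with only about 15 subjects planned per arm.

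**Working it through.** **Inputs.** The Day, Week and weeks-elapsed rows of Table 7; the ±3-day follow-up window from footnote a; the 2, 4, 8 and 12 week timing from footnotes b and c. Visit 18 (Day 547, 78 weeks elapsed) is taken as the day of the last dose for a subject who completes treatment.

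**Step 1: recover the table's own rule.** Day = 7 × weeks elapsed + 1, and Week = weeks elapsed + 1.

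For Visits 3 to 17 the weeks elapsed are 0, 1, 2, 3, 4, 6, 8, 10, 12, 16, 20, 26, 39, 52 and 65. The rule gives Days 1, 8, 15, 22, 29, 43, 57, 71, 85, 113, 141, 183, 274, 365 and 456. All 15 match the printed row.

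The remaining columns are:

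| Visit | Weeks elapsed | Printed Week | 7 × weeks + 1 | Printed Day | (Printed Day − 547)/7 | Weeks after last dose, footnote c |
|---|---|---|---|---|---|---|
| 18 | 78 | 79 | 547 | 547 | 0 | – |
| W2 | 80 | 81 | 561 | 561 | 2 | 2 |
| 19 | 82 | 83 | 575 | 575 | 4 | 4 |
| W8 | 86 | 87 | **603** | **589** | **6** | **8** |
| 20 | 90 | 91 | 631 | 631 | 12 | 12 |

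The Day rule holds in 19 of the 20 dated columns and fails only at W8. The Week rule holds in all 20, so the conflict lies between the Day row and everything else.

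**Step 2: size of the gap.** 603 − 589 = 14 days. From Day 547, Day 589 is 42 days (42/7 = 6 weeks) and Day 603 is 56 days (56/7 = 8 weeks).

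**Step 3: can the window absorb it?** 589 ± 3 gives Days 586 to 592. 603 ± 3 gives Days 600 to 606. The windows do not meet: 600 − 592 = 8 days.

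**Step 4: is it a reading error in the file?** The columns on either side of W8 fit the Day 547 anchor exactly. Day 589 also recurs on the table's continuation page and in both copies of Table 7 in the file. A broken table would not produce that pattern.

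**The case against.** The strongest reply is that this is one misprinted cell, outweighed by the rest of the protocol. The visit's name and definition say Week 8. Both week rows agree with that, as do footnotes b and c and every section that describes follow-up. No prose says 6 weeks or mentions Day 589. Footnote a also tells sites to bring subjects back into line with weeks elapsed since first dose, and that row reads 86 for W8. Because Visit 18 itself has a ±10-day window, the Day numbers in the follow-up columns are nominal.

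Most of this stands, and it limits the harm. A reader might infer that W8 has two targets of equal authority, or that the W8 data of every completer are compromised. The documents support neither. The Day cell stands alone against many consistent statements, and nothing shows that any site or system schedules by it. Subjects who stop early are timed from their own last dose, so the printed Day does not apply to them.

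The analytic weight is also modest. W8 is one of four follow-up draws, the summaries are descriptive, no test or decision rule is set at W8, and no secondary endpoint depends on it.

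The reply does not remove the error. The Day row is printed in the schedule without any statement that the week rows take precedence, and the discrepancy is too large for the visit window to hide.

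**Conclusion.** The inconsistency is real and certain as arithmetic: Day 589 is 6 weeks after Day 547, against 8 weeks in the week rows, footnotes and text, a difference of 14 days with a ±3-day window. Its consequence is conditional. It could shift the W8 blood count, lymphocyte-subset, immunoglobulin and adverse-event assessments by about two weeks, but only for subjects who complete 78 weeks and only where scheduling follows the Day row. The documents give no evidence that any visit was mistimed.

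The calculation assumes that a completer's last dose falls on Day 547. The table's own placement of W2, Visit 19 and Visit 20 at exactly 2, 4 and 12 weeks from that day supports the assumption. Which timing is intended is for the sponsor to state. This is a correction worth making because it costs almost nothing and concerns data for the primary safety objective. It is not a threat to the trial's conclusions.

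**What to change.** Reconcile the W8 Day cell with the Week row, the weeks-elapsed row, footnotes b and c and the follow-up text, so that the visit has one target. If the sponsor confirms the 8-week timing, the Day number that matches the table's own rule is 603. Any other intention would require the week rows, the visit definition, the footnotes and the text to change instead.

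Confirm that site calendars and EDC visit windows use the reconciled target. For any W8 visit already done off that target, report the results by actual days since last dose.

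If the week rows and text are kept, the cost is one table cell and a short clarification to sites and data management. No sample size, power or significance level is affected.

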9.5.2.2 Description of Procedures/Assessments Schedule

Please refer to [Table 6](#) and [Table 7](#) for the timings of the procedures and assessments to be performed during the study. Screening assessments will be organized into 4 tiers (see [Table 6](#), [Section 9.5.2](#), and [Figure 2](#)).

See [Section 9.5](#) for a full description of the procedures and assessments to be performed during this study.

[Table 8](#) presents the number of blood and CSF samples, and the total volume of blood and CSF that will be collected throughout the study. Additional samples may be taken at the discretion of the investigator if the results of any tests fall outside reference ranges or if clinical symptoms necessitate testing to ensure subject safety.

Table 8 Summary of Blood and CSF Sample Volumes

| Assessment | Total number of collection time points | Number of time points x volume per collection (mL whole blood or CSF) | | Total volume (mL whole blood or CSF) |
|--|--|---|---------------------------------|--------------------------------------|
| | | Screening and Baseline Periods | Treatment and Follow-Up Periods | |
| Blood | | | | |
| Chemistry | 12 | 2 x 2 mL | 10 x 2 mL | 24 mL |
| Hematology | 20 | 2 x 5 mL | 18 x 5 mL | 100 mL |
| Lymphocyte subset analyses ^a | 20 | 2 x 4 mL | 18 x 4 mL | 80 mL |
| PBMC | 4 | 1 x 16 mL | 3 x 16 mL | 64 mL |
| IgA, IgM, IgG | 10 | 2 x 2 mL | 8 x 2 mL | 20 mL |
| PT, PTT for INR | 2 | 2 x 3 mL | None | 6 mL |
| Thyroid function tests (thyroid stimulating hormone, free triiodothyronine and free thyroxine) | 1 | 1 x 3 mL | None | 3 mL |
| Viral screen (Hepatitis B and C) | 1 | 1 x 4 mL | None | 4 mL |
| Viral characterization | 1 | 1 x 4 mL | None | 4 mL |
| Vitamin B12 | 1 | 1 x 2 mL | None | 2 mL |
| Serum pregnancy test | 1 | 1 x 2 mL | None | 2 mL |
| Tuberculosis (interferon-gamma release assays) | 1 | 1 x 3 mL | None | 3 mL |
| Sample for immune status | 8 | 1 x 4 mL | 7 x 4 mL | 32 mL |
| PD sample | 9 | 1 x 4 mL | 8 x 4 mL | 36 mL |
| PK analysis | 7 | 1 x 3 mL | 6 x 6 mL | 39 mL |
| Pharmacogenetic sample | 1 | 1 x 3 mL | None | 3 mL |
| All blood samples, total volume whole blood collected | | 80 mL | 342 mL | 422 mL |
| CSF (For subjects who consent to CSF sample collection) (revised per Amendment 02) | | | | |
| PD and PK samples | 3 | 1 x 12 mL | 2 x 12 mL | 36 mL |

CSF = cerebrospinal fluid, Ig = immunoglobulin, INR = International Normalized Ratio, PBMC = peripheral blood mononuclear cell, PD = pharmacodynamics, PK = pharmacokinetic, PT = prothrombin time, PTT = partial thromboplastin time.

a: Whenever unscheduled lymphocyte subset tests are performed or whenever scheduled lymphocyte subsets are repeated, a CBC with differentials must also be performed. Therefore, for each unscheduled or repeat test, an additional 9 mL will be collected (5 mL for hematology and 4 mL for lymphocyte subset analyses)
(Table 8 revised per Amendment 04)

9.5.3 Appropriateness of Measurements

All clinical assessments are standard measurements commonly used in studies of AD.

Standard safety assessments incorporated into this protocol include vital signs, clinical laboratory assessments, physical examinations, ECG measurements, and reports of AEs. MRI will be used to detect vasogenic edema, macrohemorrhage, an area of superficial siderosis, or a symptomatic microhemorrhage and is a standard evaluation to ensure subject safety. The C-SSRS has been endorsed by the FDA as a measure of potential suicidality ([Guidance for Industry Suicidality](#)).

A number of safety aspects have been built into the design of this study in light of the preclinical and clinical safety data with E2609, in addition to mitigating clinical risk in the progression from 14 days of dosing in the MAD study to 18 months of treatment in this Phase 2 study. Details are provided in [Section 9.2.5](#).

9.5.4 Reporting of Serious Adverse Events, Pregnancy, and Events Associated with Special Situations

9.5.4.1 Reporting of Serious Adverse Events

All SAEs, regardless of their relationship to study treatment, must be reported on a completed SAE form by email or fax as soon as possible but no later than 24 hours from when the investigator becomes aware of the event.

SAEs, regardless of causality assessment, must be collected up to 3 months after the last dose of study drug, ie, through to the final follow-up visit (Visit 20). (revised per Amendment 04) (revised per Amendments 04 and 05) However, any SAEs volunteered by subjects after this time point must be reported according to standard procedures. All SAEs must be followed to resolution or, if resolution is unlikely, to stabilization. Any SAE judged by the investigator to be related to the study treatment or any protocol-required procedure should be reported to the sponsor regardless of the length of time that has passed since study completion.

The detailed contact information for reporting of SAEs is provided in the Investigator Study File.

For urgent safety issues, please ensure all appropriate medical care is administered to the subject and contact the appropriate study team member listed in the Investigator Study File.

It is very important that the SAE report form be filled out as completely as possible at the time of the initial report. This includes the investigator's assessment of causality.

Any follow-up information received on SAEs should be forwarded within 1 business day of its receipt. If the follow-up information changes the investigator's assessment of causality, this should also be noted on the follow-up SAE form.

Preliminary SAE reports should be followed as soon as possible by detailed descriptions including copies of hospital case reports, autopsy reports, and other documents requested by the sponsor.

The investigator must notify his/her IRB/IEC of the occurrence of the SAE in writing, if required by their institution. A copy of this communication must be forwarded to the sponsor, or its designee, to be filed in the sponsor's Trial Master File.

9.5.4.2 Reporting of Pregnancy and Exposure to Study Drug through Breastfeeding

Any pregnancy in which the estimated date of conception is either before the last visit or within 28 days of last study treatment, or any exposure to study drug through breastfeeding during study treatment or within 28 days of last study treatment, must be reported.

If an adverse outcome of a pregnancy is suspected to be related to study drug exposure, this should be reported regardless of the length of time that has passed since the exposure to study treatment.

A congenital anomaly, death during perinatal period, an induced abortion, or a spontaneous abortion are considered to be an SAE and should be reported in the same time frame and in the same format as all other SAEs (see Reporting of Serious Adverse Events [[Section 9.5.4.1](#)]).

Pregnancies or exposure to study drug through breastfeeding must be reported by fax or email as soon as possible but no later than 1 business day from the date the investigator becomes aware of the pregnancy. The contact information for the reporting of pregnancies and exposure to study drug through breastfeeding is provided in the Investigator Study File. The Pregnancy Report Form must be used for reporting. All pregnancies must be followed to outcome. The outcome of the pregnancy must be reported as soon as possible but no later than 1 business day from the date the investigator becomes aware of the outcome.

A subject who becomes pregnant must discontinue study treatment.

